10.1.3 AE and SAE Summary Table

10.1.4 Forms

We will utilize MedWatch for adverse event reporting. A copy of this form is provided in **Appendix F**.

10.1.5 Secondary Malignancies

Investigators are required to report secondary malignancies occurring on or following treatment on NCI sponsored protocols using the form noted above. **Exception:** Cases of secondary AML/MDS are to be reported using the NCI/CTEP Secondary AML/MDS Report Form.

10.2 Data Reporting

This study will be under the supervision of an external Data and Safety Monitoring Committee without conflicts of interest who will be appointed and chartered to oversee the review of all adverse events and efficacy determinations. The reviews will be completed quarterly and in real time. The committee will also oversee the clinical trial data analysis and publication of study results. The DSMB will be comprised of a medical infectious disease expert, a neurosurgeon familiar with oncolytic virus therapy for brain tumors, a neuro-oncologist familiar with oncolytic virus therapy for patients with brain tumors and an expert in the use of current molecular biology techniques for the detection and quantification of Herpes Simplex Virus in clinical specimens. The Medical Monitor is a medical infectious disease expert. Any member who resigns or otherwise leaves service on the DSMB will be replaced by an expert with equivalent experience and expertise and without any potential conflicts. The Data and Safety Monitoring Board for this Phase I study will utilize the appended NCI-approved Data and Safety Monitoring Plan (**Appendix G**).

10.3 CTEP Multicenter Guidelines:

Not applicable.

10.4 Cooperative Research and Development Agreement (CRADA)/Clinical Trials Agreement (CTA):

Not applicable.

11. STATISTICAL CONSIDERATIONS

We will implement the CRM design (the dosing range is described previously in this protocol) in a manner similar to that of Geletneky et al. [43] We will define the primary criterion for dose modification as the relative frequency of a DLT at a given dose level. A dose will be considered as tolerable if the probability of toxicity is ≤33%. The Recommended Phase 2 Dose (RP2D) will be the dose level with the highest posterior probability of having a toxicity of ≤33%. The Optimal Biologic Dose (OBD) will be the RP2D that is obtained by enrolling the fewest number of evaluable patients possible. The posterior probability for toxicity will be determined using a logistic model, where the toxicities will be parameterized as probabilities in the model. When a patient enters the study, the dose level will be determined by calculating the posterior probability for each dose level to be tolerable. The highest dose level that is tolerable will be allocated. Regarding the dose escalation scheme, a conventional three-at-one [44] design will be used as long as no DLT is observed. After the first DLT is observed, one additional patient will be enrolled at the same dose before the dose will be determined as the RP2D using the logistic model. The highest dose with a median probability of at least 33% will be applied as the current RP2D to the subsequent patient, following the CRM [45]. If the RP2D is calculated as dose level -1 (i.e. 1×10^4 PFU), the trial will end with no safe dose established.

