1.4 Tertiary Objectives

1.4.1 To delineate the local and systemic immune response to M032 administration.

1.4.2 To characterize the *in situ* biologic activity of M032 after intratumoral inoculation, where possible.

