4.1.2 Estimated Number of Patients

Moving forward, we anticipate as few as four and as many as 20 additional patients could be enrolled and treated in this trial. We expect approval of the use of the four already enrolled and treated patients to seed the model, which would bring the overall total range from 8- 24 patients. If the highest planned dose is successfully administered to subjects and assuming one subject per CRM-calculated dose level (10), and an additional 10 subjects will be entered at the CRM-estimation of the safe target dose ($10+10 = 20$). If all subjects develop DLTs, the CRM model would de-escalate both through the initial and the two lower dose levels involving no more than 4 subjects and the trial would be halted (Section 4.5) with a minimal accrual of 4 subjects. Assuming that no DLTs will be encountered, we expect that under optimal conditions only 20 subjects ($10+10$) will be enrolled and treated in this study. These numbers will be modified if the new patient data for seeding the model is approved and could even decrease.

Thus, the maximum number of subjects that we expect to enroll and treat in this trial would be 20, assuming that the CRM will adjust each dose after the first 2 or 3 subjects and as more subjects are enrolled to encompass the initial test range. On the other hand, the minimum number of subjects who could be enrolled in this trial would be 4 assuming 2 DLTs at Dose Level 1, and the CRM recommending one or two lower doses.

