4.5 Halting Rules for Study

Should 2 or more Grade 3 or Grade 4 toxicities not thought to be related to tumor, prior therapy or expected to be related to HSV occur in the same dose level, enrollment will be suspended until an evaluation of these toxicities has been conducted by the trials Data Safety and Monitoring Board (DSMB). The DSMB will be the arbiter as to whether these toxicities can be attributed to M032 and if so, invoke a stopping rule, halting enrollment. If the DSMB should feel that these toxicities are not related to M032 administration, enrollment will be reinstated as per its instructions. Should a particular DLT be evaluated by the DSMB and felt to be 1) consistent with M032 activity and 2) of acceptable duration and severity, the DSMB may decide to waive the DLT and/or enroll additional patients at this dose level due to the life-threatening nature of the underlying disease under study.

- The DSMB may interrupt study enrollment and entry at any time if medically indicated.
- If one (1) subject dies due to an event related to (caused by) the study intervention, study enrollment will be halted and enrollment may only begin after the DSMB reviews the data and the DSMB determines it is safe to continue.
- If two (2) subjects experience a Grade 4 toxicity using the NCTAE Toxicity Table, study enrollment will be halted and enrollment may only begin after the DSMB determines it is safe to continue.
- If two (2) instances of cytokine storms result in two instances of Grade 4 toxicity and/or uncontrolled corticoid steroids and acyclovir therapy are required, within the same cohort, study enrollment will be halted and enrollment may only begin after the DSMB reviews the data and the DSMB determines it is safe to continue.

- If two (2) or more grade 3 toxicities not thought to be related to tumor, prior therapy or expected to be related to HSV occurring in the same dose cohort, enrollment will be suspended until an evaluation of these toxicities has been conducted by the trial's DSMB. Enrollment may only begin after the DSMB reviews the data and the DSMB determines it is safe to continue.

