7. CORRELATIVE/SPECIAL STUDIES

To address secondary objectives of the protocol, additional correlative studies will be performed on blood/serum, conjunctival secretions, saliva samples and tumor tissue samples.

Blood Samples: Blood samples (heparinized) will be taken at Baseline, on Days 0, 2, 3, 10, 28 and at Months 3, 6, 9 and 12. One ml of each sample will be submitted to the Clinical Virology Diagnostic Laboratory for HSV culture to determine the amount of virus shedding. The balance of the blood sample will be separated by density gradient centrifugation to provide plasma (serum) and peripheral blood mononuclear cells (PBML). Plasma will be tested to permit detection and quantification of HSV antibody titer pre-and post-inoculation via ELISA. Peripheral blood mononuclear leukocytes will be quantified for subsets and other leukocyte markers by FACS analysis, expression of activation signals (intracellular lymphocyte interferon-gamma levels) and lymphocyte transformation assays will also be performed to assess aspects of the T_H1 response to treatment with M032. Plasma cytokine assays will be performed to quantify changes over time from baseline. Conjunctival, blood and saliva will be assessed for HSV shedding by standard culture methods. Any positive cultures will be further

characterized for wild-type or M032 HSV by PCR. Any remnant blood will be stored for future brain tumor research.

Tissue Samples: If available, remnant brain tissue from the biopsy will be snap-frozen in liquid nitrogen and stored for future research. Should any patient with recurrent tumor after HSV treatment be determined to benefit from additional tumor resection for diagnosis or to ameliorate intractable symptoms caused by increased mass effect and intracranial edema, the tumor will be removed *en bloc* as much as possible and sectioned in 2-4mm thick slices perpendicular to the placement of the catheters. Each section will be cut into quarters and each quarter will be labeled 1, 2, 3 or 4, processed and stored for future research as follows:

Quarter 1: Snap freeze in liquid nitrogen for immediate assessment of viral replication *in vitro*.

Quarter 2: Snap freeze in liquid nitrogen for RNA and DNA extraction and the following evaluations:

- Quantitative PCR (vector replication *in-vivo*; compare number of copies to vector input)
- RT-PCR to detect HSV polymerase mRNA (vector replication *in-vivo*)

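### Section 11's Optimal Biologic Dose is the toxicity-based RP2D under another name: whenever an RP2D is declared, an OBD is declared with it, whatever the biologic data show

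*Combined protocol and SAP*

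**What the plan says.** Section 11 builds the OBD in three steps.

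- Tolerability: "A dose will be considered as tolerable if the probability of toxicity is ≤33" per cent.
- RP2D: "The Recommended Phase 2 Dose (RP2D) will be the dose level with the highest posterior probability of having a toxicity of ≤33" per cent.
- OBD: "The Optimal Biologic Dose (OBD) will be the RP2D that is obtained by enrolling the fewest number of evaluable patients possible".

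Biologic activity is treated elsewhere as a question of its own. Section 1.4 has the tertiary objective "To delineate the local and systemic immune response to M032 administration", and a second one on in situ activity. Section 7 adds: "Plasma cytokine assays will be performed to quantify changes over time from baseline". The Section 8 calendar schedules serum IL-12, IFN-gamma and LTA/Elispot samples pre-study, on Days 2, 3, 10 and 28, and at Months 3, 6, 9 and 12.

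The plan also has ways to finish without an RP2D. If the RP2D is calculated as dose level -1, Section 11 says "the trial will end with no safe dose established". If all subjects have DLTs, Section 4.1.2 says "the trial would be halted (Section 4.5) with a minimal accrual of 4 subjects". Section 4.5 allows the DSMB to "invoke a stopping rule, halting enrollment" for toxicity that it attributes to M032.

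**The concern.** A dose called biologically optimal would ordinarily be chosen, at least in part, on a measure of biologic effect. Here the label comes from a toxicity criterion and an enrolment count. M032 is meant to work partly by inducing an immune response through IL-12, and Section 2.3 says that the local effect of IL-12 in human glioma is unknown. Activity therefore cannot be presumed to rise with dose, or to be present at all.

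Section 4.1.1 looks ahead to a phase II trial. A reader of the final report who meets the term OBD would reasonably take it to mean that the assays supported that dose. Under the present sentence the label would be attached just the same if the assays were flat, or if they levelled off at a lower dose.

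**Working it through.** The plan gives no figure on this point, so the check is a logical one on the chain of definitions.

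**1. Write the rule as a function.** Let D be the DLT data by dose (with the model's starting data), n the number of evaluable patients, and B all biologic results.

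- RP2D = f(D), from the Section 11 definition.
- OBD = RP2D, qualified by the smallest n.
- B appears in neither line.

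**2. Test the qualifier.** One completed trial yields one RP2D and one n. With no second pair to compare, choosing the smallest n selects nothing. The phrase describes the efficiency of the design, not a property of a dose. So OBD = f(D).

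**3. Vary the biology.** For any two sets of biologic results B1 and B2 with the same D, the OBD is the same. Hence:

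- P(OBD declared | RP2D declared) = 1
- P(OBD = RP2D | RP2D declared) = 1
- P(OBD declared | no RP2D) = 0

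These hold with no activity at any dose and with any dose-response shape. Section 4.1.1 lets investigators use judgement in assigning the next dose. That can change which doses contribute to D, but not the definition.

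**4. Check whether an OBD must always appear.** It need not. The exits in Sections 11, 4.1.2 and 4.5 end the trial, or stop enrolment, on toxicity. As a size check, suppose (my assumption) independent patients with the same DLT rate p at every dose. The all-DLT path of four subjects in Section 4.1.2 has probability p^4:

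- p = 0.33: 0.33^4 = 0.012
- p = 0.80: 0.80^4 = 0.41

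An illustrative two-parameter logistic CRM was also run. It was seeded with Table 1 and targeted 1/3. It started at log10 dose 5 with a maximum of 9, capped steps at 1 log, rounded to 0.5 and treated at most 20 patients. It stopped without a dose when the recommendation fell to log10 4 or below. The share of runs naming a dose was 100% at an assumed flat DLT rate of 0%, about 58% at 33%, and 0% at 100%. In this simplified version a DLT in the first patient ends the run, which is stricter than the plan's four-subject minimum. The middle figure is therefore not an estimate for this trial. The two extremes are enough to show that naming a dose depends on toxicity.

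**5. Look for text that changes the definition.**

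| Place | What it does | Link to the OBD |
|---|---|---|
| Synopsis endpoints; Sections 1.2 to 1.4 | List endpoints and objectives | OBD not mentioned |
| Section 4.1.1, end | PFS or OS may inform the phase II dose if an MTD is not being reached | Optional; OBD not mentioned |
| Section 11.1 | Immunologic change from baseline, with plots by dose group | Descriptive only |
| Section 11.4.1 | Shedding and antibody frequencies by cohort | Descriptive only |

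In the public text the term OBD occurs only in Section 11, and none of these places supplies a biologic criterion for it.

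**The case against.** The strongest reply is that the term does almost no work. It is not an objective or an endpoint, it assigns no dose, and it triggers no test or stop. Nor would the label hide a plateau from a careful reader, because Sections 11.1 and 11.4.1 still report immunologic, shedding and antibody data by dose group or cohort. Section 4.1.1 also shows that the phase II dose is not tied to the OBD: if toxicities are too many or too few to reach an MTD, PFS or OS may be taken into account. All of this stands, and it limits the point to one of labelling. It does not supply a biologic basis for the label. The Section 4.1.1 provision is optional, conditional on not reaching an MTD, and concerns PFS and OS rather than the collected immune markers.

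A reader might infer two stronger things that the documents do not support.

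- *That the trial will name an OBD come what may.* It will not: the no-safe-dose exit and the halts can leave no RP2D and therefore no OBD.
- *That the label will land on the highest dose, well above where activity levels off.* The plan gives no dose-activity data, so any plateau would be invented. The location also depends on how the RP2D sentence is read. Under an increasing toxicity curve, the probability that toxicity is at or below 33% is greatest at the lowest dose, whereas the synopsis points to the maximal planned dose if no DLT is seen. The present point needs neither reading, because no biologic input enters under either.

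**Conclusion.** The point holds in a limited form. Conditional on an RP2D being declared, an OBD is declared at the same dose with probability 1, and no biologic result can alter or withhold it. This follows from the wording of Section 11 alone and needs no assumption about DLT rates or about the shape of any biologic response. The assumed DLT rates above serve only to show that toxicity can prevent the declaration.

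The practical effect is confined to reporting and to how the dose might be described in later planning: a dose called biologically optimal without biologic evidence. Patient dosing, the primary endpoint and the planned descriptive analyses are unaffected. The sentence is worth correcting because it sits in the statistical section and the correction is nearly free.

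**What to change.** Delete the OBD sentence from Section 11. Report the RP2D and state plainly that it rests on toxicity alone. Present the biologic data already collected (serum IL-12, IFN-gamma, LTA/Elispot, other cytokines, HSV antibody and shedding) descriptively by dose, labelled exploratory. Where Section 4.1.1 allows PFS or OS to inform the phase II dose, make clear that this is a separate, optional consideration and does not define an OBD.

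I would not replace the sentence with a marker-threshold rule. Section 4.1.1 sets a dose cohort size of 1 and Section 4.1.2 gives an overall range of 8 to 24 patients. A threshold applied dose by dose would rest on very few observations, and the plan offers no criterion for it.

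The cost is one sentence removed and one short clarification, with no new data, patients or procedures. The downside is that the trial ends without a dose it can call biologic.

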$$P(\text{toxicity}|\text{dose}) = \frac{1}{1 + e^{-\beta(\text{dose}-d_{50})}}$$

where β is the “slope” of the curve and d_{50} the midpoint (or dose that yields a 50% response). The parameters β and d_{50} govern the dose finding process, and are estimated, denoted by $\hat{\beta}$ and \hat{d}_{50} , initially by clinical judgment and afterwards by the observed data. This represents a second subjective component of dose finding designs.

Classical dose-ranging designs incorporate this component of subjectivity by setting out, in advance of the experiment, a set of doses to employ. A strictly Bayesian approach to the CRM requires a joint prior probability distribution for the parameters β and d_{50} . However, we have found it easier for clinicians to render their clinical judgment about β and d_{50} in the form of pseudo-data. Specifically, we ask for two points on the dose toxicity curve: the dose thought to yield a 10% probability of toxicity (d_{10}) and the dose thought to yield a 90% probability of toxicity (d_{90}). Two points, d_{10} , d_{90} , are required to initiate the fit for a two-parameter model. The exact points chosen are arbitrary, but we have found these generally work well or are easily adapted. The d_{10} point can often be discarded after some data have been obtained. The d_{90} point is necessary to obtain a fit of the model, but is usually relatively unimportant because it characterizes a region of the model that does not heavily influence prediction of the next dose. In this sense, d_{90} is a nuisance parameter – necessary for model fitting, but relatively uninfluential on the dose escalation.

At both d_{10} and d_{90} , the investigator specifies a numerator (number of responses) and denominator (number of subjects treated), such that numerator/denominator = 0.1 or 0.9 as the case may be. The denominators are always taken to be small numbers, e.g. 1, to represent weak evidence and reduce the influence of these points compared to real subject data.

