Table 1: Initializing Data used to start the CRM			
Log Dose	N	r	Weight
4	1	0.05	0.5
5	1	0.10	0.5
6	1	0.2	0.5
7.5	1	0.5	0.5
9	1	0.8	0.5
10	1	0.9	0.5
12	1	1	0.5
15	1	1	0.5

(Initial recommended dose based on these data=6.7842)

$$L(\beta, d_{50}) = \sum_{i=1}^k \left[\log \binom{n_i}{r_i} - n_i \log(1 + e^{-\beta(d_i - d_{50})}) - (n_i - r_i) \log(1 + e^{-\beta(d_i - d_{50})}) \right]$$

could suggest that the current value for d_{10} and/or d_{90} is inappropriate. We would not proceed blindly with a CRM (or any other) dose escalation in such a circumstance. All testing doses will be the estimated dose round-down to the nearest 10th.

For each subsequent level, the investigators will evaluate the recommended dose-level. It is possible that the model may recommend large interval increases in dose level with which the investigators do not feel comfortable. In these cases, the investigators will use this information and their best clinical judgment to assign a next dose level. We emphasize that the dose levels recommended by the CRM should not be taken literally.

Model based dose escalation methods, especially the CRM, are able to account for ordinal or quantitative toxicity assessments, and use this information to guide subsequent dose changes. In particular, the binomial likelihood is

where i indexes the dose level, p is the probability of toxicity (equation 1 above), d is dose, n the number of subjects treated at each dose, and r the number of toxicities. While n is constrained to be an integer, r does not have to be integral. In particular, r can be taken to be the sum of ordinal or quantitative toxicity measures provided that $r < n$. The maximization of equation 2 with respect to the parameters (model fitting) can then proceed in the usual fashion. Furthermore, the ordinal scores need not be the same for all types of toxicity. For example, we might not want alopecia to have the same effect on dose reduction as neurologic toxicities.

Table 2: Six Different CRM-defined Dose Escalation Scenarios

Subject #	S1	S2	S3	S4	S5	S6
1	5	5	5	5	5	5
2	6	6	6	6	6	6
3	7	7	7	7	7	7
4	7.5	7.5	7.5	7.5	7.5	7.5
5	8	8	8	8	8	8
6	8	8	8	8	8	8
7	8.5	8.5	8.5	8.5	8.5	7.5
8	9	9	9	9	8	8
9	9	8.5	9	9	8.5	8
10	9	8.5	9	9	8.5	8
11	9	8.5	9	8	8.5	8.5
12	9	8.5	9	8.5	9	8.5
14	9	8.5	9	8.5	9	9
15	9	8.5	9	8.5	9	9
16	9	8.5	9	8.5	9	9
17	9	8.5	8.5	8.5	9	9
18	9	8.5	8.5	8.5	9	9
19		8.5	8.5	8.5	9	9
20			8.5	8.5	9	9
MTD	9	8.5	8.5	8.5	9	9

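### Section 11 makes dose assignment and the RP2D depend on posterior probabilities, but the plan specifies only a likelihood fit with pseudo-data and gives no base prior or cut-off

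*Combined protocol and SAP*

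**What the plan says.** Section 11 (Statistical Considerations) sets both key decisions in posterior terms.

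- Allocation: "When a patient enters the study, the dose level will be determined by calculating the posterior probability for each dose level to be tolerable". Each patient then receives the largest dose judged tolerable.
- RP2D: "The Recommended Phase 2 Dose (RP2D) will be the dose level with the highest posterior probability of having a toxicity of ≤33" per cent.
- Source of the posterior: "The posterior probability for toxicity will be determined using a logistic model, where the toxicities will be parameterized as probabilities in the model". No prior is named.
- A second RP2D rule, for use after the first DLT: "The highest dose with a median probability of at least 33% will be applied as the current RP2D to the subsequent patient".

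Section 4.1.1 (Continual Reassessment Method) describes something else. It notes that "A strictly Bayesian approach to the CRM requires a joint prior probability distribution for the parameters" (slope and d50), and then departs from that approach: "we have found it easier for clinicians to render their clinical judgment about" those parameters as pseudo-data. The parameters are estimated "initially by clinical judgment and afterwards by the observed data". Table 1 lists eight pseudo-observations, each with weight 0.5. Fitting is by likelihood: "The maximization of equation 2 with respect to the parameters (model fitting) can then proceed in the usual fashion". The only model output stated is a point estimate, an initial recommended log dose of 6.7842.

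**The concern.** A maximum-likelihood fit returns one value of the slope, one value of d50 and hence one estimated DLT probability per dose. It does not return a distribution, so it provides neither a posterior probability that a dose is tolerable nor a posterior median. Section 11 needs those quantities for every patient and for the final recommendation.

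The primary endpoint is the CRM-estimated highest safe dose, from at most 24 patients assigned one at a time. With so few patients, prior information carries real weight. If the analyst has to supply a prior and a cut-off, part of the primary result rests on choices the plan does not contain, and those choices could be made after DLTs have been seen.

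**Working it through.** **1. The plan's own figure.** Inputs are the eight rows of Table 1 (log dose, r): 4, 0.05; 5, 0.10; 6, 0.2; 7.5, 0.5; 9, 0.8; 10, 0.9; 12, 1; 15, 1. Each has N = 1 and weight 0.5. The model is p(d) = 1/(1 + exp(−β(d − d50))), fitted by maximising the weighted binomial likelihood.

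Result: β = 0.919, d50 = 7.461. The dose with p = 1/3 is d50 − ln 2/β = 7.461 − 0.693/0.919 = 6.71. The plan states 6.7842, which this fit does not reproduce. What follows is therefore an illustration and is not shown to match the trial software.

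**2. The likelihood rule with data.** Assume no DLT in four subjects at log doses 5, 6, 7 and 7.5, each with weight 1. The fit gives β = 1.291, d50 = 8.511.

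- 1/3 point: 8.511 − 0.693/1.291 = 7.97.
- p(8) = 1/(1 + exp(1.291 × 0.511)) = 0.341.
- p(7.5) = 1/(1 + exp(1.291 × 1.011)) = 0.213.

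Rounding to the nearest 0.5, as one sentence of Section 4.1.1 says, gives 8. Rounding down to one decimal, as another sentence there says, gives 7.9. Requiring a fitted probability of at most 33% on the half-log grid gives 7.5.

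**3. The posterior rule with the same data.** The required quantity is P(p(d) ≤ 0.33 | data) = ∫∫ 1[p(d) ≤ 0.33] L π / ∫∫ L π, where L contains the pseudo-data and the four subjects, and π is a base prior that the plan does not give. The priors and cut-offs below are assumptions.

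| Assumed base prior | P at 7 | P at 7.5 | P at 8 | Dose at cut-off 0.5 | Dose at cut-off 0.8 |
|---|---|---|---|---|---|
| Flat on intercept and slope | 0.926 | 0.752 | 0.475 | 7.5 | 7 |
| Uniform: d50 on 4–15, slope on 0–3 | 0.845 | 0.708 | 0.529 | 8 | 7 |
| Uniform: d50 on 4–15, slope on 0–5 | 0.861 | 0.715 | 0.517 | 8 | 7 |

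Two other assumed priors give 0.377 at log dose 8 (normal on intercept and log slope) and 0.529 (d50 uniform, slope exponential). They also select 7.5 and 8 at a cut-off of 0.5. The exponential version just misses 0.8 at log dose 7 (0.781).

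**4. A default flat prior does not fill the gap.** Take a prior flat on d50 and slope, the plan's own parameters. The normalising constant keeps growing as the lower limit of log slope goes from −4 to −8, −16 and −32: 0.96, 1.03, 1.16, 1.44. The posterior is improper unless the analyst adds bounds.

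**5. Section 11's selection wording, taken literally.** With β > 0, the event p(d) ≤ 33% is the same as d lying at or below the 33% point of the curve. Its probability therefore falls as d rises. Under the flat prior above it is 0.997 at log dose 5, 0.926 at 7 and 0.126 at 9. The dose with the highest such probability is always the lowest on offer. The median rule runs the other way: it asks for a median toxicity of at least 33%, whereas Section 11 calls a dose tolerable at 33% or less. On a rising curve, the highest dose meeting an at-least-33% condition is the top dose whenever any dose meets it.

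**The case against.** The strongest reply is that pseudo-data are a recognised way to encode prior information, and Table 1 supplies them with weights. A reader might infer that the posterior quantities cannot be computed at all. That goes too far: step 3 computes them once a base prior is assumed. What stands is that the plan neither says the pseudo-data serve as a prior nor supplies the rest.

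A reader might also infer that the two sections demonstrably assign different doses, or that the RP2D is a full log out. The documents do not support either. With nearest-0.5 rounding, the likelihood dose (8) equals the dose under both uniform priors. With an at-most-33% rule, it equals the flat-prior dose (7.5). The half-log gap thus depends on rounding as much as on the estimator. The full log arises only with a cut-off of 0.8, which appears nowhere in the plan. Comparisons before any data assign no dose, because the starting dose is fixed.

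Finally, Section 11 may be loose wording for the likelihood rule. It calls a dose tolerable at 33% or less, allocates the highest tolerable dose, and cites the same CRM source as Section 4.1.1. The Table 2 path in scenario S1 agrees with a point-estimate rule at eight of nine steps. That reading is plausible and lowers the operational risk, and it also makes it implausible that anyone would follow the lowest-dose rule in practice. It does not remove the conflict: posterior and median are used as decision quantities, and the other trial design that Section 11 follows is cited, not set out.

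**Conclusion.** The concern holds in a limited form. Sections 4.1.1 and 11 describe two different rules for the primary result, and the rule in Section 11 cannot be carried out from what the plan specifies. Two of its selection statements also contradict the plan's own 33% criterion; this needs only a dose-toxicity curve that rises with dose.

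The numerical size is illustrative. In the assumed case of no DLT in four subjects, the candidate dose is 7.5 or 8 at a cut-off of 0.5, and 7 at 0.8 under the three priors tabulated. These figures rest on assumed priors, assumed cut-offs, an assumed outcome pattern, Table 1 weights of 0.5, and a fit that gives 6.71 where the plan states 6.7842. They show that the plan leaves the dose undetermined. They do not show that any particular dose would be wrong.

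**What to change.** Reconcile Section 11 with Section 4.1.1 so that one estimator and one decision rule, including one rounding convention, govern both allocation and the RP2D. There are two coherent routes, and the choice is the sponsor's:

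- Remove the posterior and median wording from Section 11, refer to the likelihood-based CRM of Section 4.1.1, and report an interval for the DLT probability at the selected dose.
- Or specify the prior (stating whether the pseudo-data form part of it, and with what weight), the posterior cut-off and the computation, and remove the maximisation text from Section 4.1.1.

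Under either route, correct the highest-posterior-probability and at-least-33% statements so that they agree with the plan's own criterion of 33% or less.

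The first route is mainly redrafting and leaves the fitting method of Section 4.1.1 as it is. The second also requires choosing and checking a prior and cut-off, and matching the software to them. Both need an amendment. The same edit should reconcile the two rounding sentences in Section 4.1.1, and Section 11's three-at-one scheme with the cohort size of one in Section 4.1.1. No new patient data are needed.
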